5.7.3.1 Pharmacokinetics

Plasma concentration measurements of AKST4290 and the major metabolites M227 and M373 will be collected to assess systemic exposure to the study agent. Pharmacokinetic samples will be collected immediately prior (-15 min) to study drug administration at Baseline and Weeks 2, 4, 8, 12, and 14, as well as 1 hour and 2 hours after administration at Baseline and Weeks 4 and 12. A final PK sample will be collected at Follow-Up (Week 14). Concentration of AKST4290 in plasma will be summarized descriptively at each visit timepoint.

5.7.3.2 Wearable Sensor Device

A wearable sensor device allowing for the continuous measurement of health-related symptoms, including the motor and nonmotor features of bradykinesia, tremor, general activity, and sleep, will be provided to applicable subjects at Screening, Week 4, and Week 8. Data will then be collected over a 6-day period and returned at the following visit (i.e. Baseline, Week 8, and End of Treatment). Bradykinesia, tremor, general activity, and sleep parameters will be summarized descriptively at each applicable timepoint.

To evaluate change from baseline, the same MMRM model used to evaluate the primary endpoint will be employed to produce LS means, SE, and 95% CIs of the LS means for each treatment arm at each scheduled

visit. The unadjusted mean change from baseline, and the difference in LS means between treatment arms and 95% CI of the difference will also be calculated.

5.8 Safety Analyses

Safety analysis includes study drug accountability, incidence and severity of treatment emergent adverse events, laboratory parameters, vital signs, 12-lead ECG, physical examination, pregnancy tests, and prior and concomitant medications. Unless otherwise specified, safety parameters will be summarized by treatment group using the safety population.

5.8.1 Study Drug Accountability

The number of subjects receiving daily doses of 800 mg of study medication will be summarized over the entire course of study treatment and between baseline and Week 4, Week 4 and Week 8, and Week 8 and End of Treatment (Week 12) by treatment group, for the safety population. The number of subjects with missed or additional doses will also be summarized.

5.8.2 Adverse Events

All TEAEs will be reported. A TEAE is defined as an AE that occurs on or after the date of the first study treatment.

A summary of all TEAEs by the number and percentages of subjects who experienced any of the following will be provided:

- Any TEAE, including severity (Mild, Moderate, and Severe), and relationship to study treatment (Unrelated, Possibly Related, Definitely Related), and AEs leading to discontinuation of study participation.
- Any serious TEAE, including severity (Mild, Moderate, and Severe), and relationship to study treatment (Unrelated, Possibly Related, Definitely Related), and AEs leading to discontinuation of study participation.
- Any event of Special Interest (AESI).
- Any fatal TEAEs, including relationship to study treatment (Unrelated, Possibly Related, Definitely Related).

5.8.2.1 Summary for All TEAEs

The number and percentage of subjects who experience TEAEs will be tabulated by SOC and PT using the MedDRA dictionary. Adverse events will be counted only once for a subject within each PT and SOC; thus, since a subject may have more than one PT within a SOC, percentages of PT may not sum to the percentages in the SOC.

For all TEAEs the following will be summarized:

- Overall summary of any TEAEs, presented by SOC/PT

- Overall summary of any TEAEs by worst severity, presented by SOC/PT
- Overall summary of any TEAEs by closest relationship to study treatment, presented by SOC/PT

A listing of all AEs will be provided. This listing will include a flag identifying if an AE is a TEAE.

5.8.2.2 Summary for Serious TEAEs

For all serious TEAEs the following will be summarized:

- Overall summary of any serious TEAEs by worst severity, presented by SOC/PT
- Overall summary of any serious TEAEs by closest relationship to study treatment, presented by SOC/PT

A listing of all serious AEs will be provided. This listing will include a flag identifying if an AE is a TEAE.

5.8.2.5 Deaths

Deaths, if any, will be provided in a listing only.

5.8.3 Laboratory Data

Biological samples (e.g. whole blood, serum/plasma, urine) will be collected at all in-person visits (i.e. Visits 1-7) for laboratory evaluations. Laboratory test will include hematology, chemistry, coagulation, infectious disease serology, qualitative urinalysis, and pregnancy testing in women of childbearing potential (WOCBP). Laboratory data summaries will consist of the following:

- Observed values at screening, baseline and Weeks 2, 4, 8, 12, and 14 along with change from baseline at each scheduled post-baseline visit.
- Shift tables by treatment group and by out of range flag at Weeks 2, 4, 8, 12, and 14, compared to baseline.
- Number and percentage of subjects with abnormal laboratory tests at all visits.

The tests will be presented in the original units collected. If the original value contains the “<” sign, AVAL in the laboratory analysis dataset (ADLB) dataset will be derived by extracting the numeric value from LBSTRESC and subtracting $0.1(N+1)$ to that numeric value, where N is the number of decimals in the numeric value. For example, AVAL will be set to 0.29 if LBSTRESC = “< 0.3”. If the LBSTRESC value contains the “>” sign, AVAL in the ADLB dataset will be derived by extracting the numeric value from LBSTRESC and adding $0.1(N+1)$ to that numeric value, where N is the number of decimals in the numeric value. For example, if LBSTRESC = “>1000”, AVAL will be set to “1000.1”. Subject listings will present all data collected along with toxicity grading.

Results for chemistry, hematology, urinalysis, coagulation, infectious serology, and pregnancy tests in WOCBP will be provided in separate listings. A listing of abnormal laboratory tests will also be provided.

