3.2 Secondary Endpoints

- Incidence of treatment-emergent adverse events (TEAEs) and serious adverse events (SAEs) identified by the Medical Dictionary for Regulatory Activities (MedDRA) preferred term (PT) and grouped by MedDRA System Organ Class (SOC).
- Incidence of abnormalities or clinically-significant changes from Baseline in laboratory test data, vital sign measurements, and electrocardiograms (ECGs).

- Change from Baseline (Day 1) in clinical function, motor function, and activities of daily living at Week 12 (Day 84) during the on-medication state as assessed by:
 - MDS-UPDRS Parts 1-4
 - Montreal Cognitive Assessment (MoCA)
 - Schwab and England Activities of Daily Living (SE-ADL) Scale
 - Clinical Impression of Severity Index – PD (CISI-PD)
 - PD Quality of Life Questionnaire-39 (PDQ-39)
 - Sheehan-Suicidality Tracking Scale (S-STS)
 - 10-meter timed walk (will also be assessed in the off-medication state)
 - Hauser 3-Day Patient Diary

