4.7 Study Assessment Time Points

The study consists of 8 protocol-specified visits which will be assessed as nominal visits from an analysis perspective:

- Visit 1, Screening Visit (Day -14 to -7)
- Visit 2, Baseline (Day 1): Subjects will be randomized after eligibility has been confirmed, study drug/placebo dispensed.
- Visit 3 (Day 14 ± 2)
- Visit 4 (Day 28 ± 2)
- Visit 5 (Day 56 ± 2)
- Visit 6 – End of Treatment (EOT) (Day 84 ± 2)
- Visit 7 (Day 98 ± 3 or 14 days after Early Termination)
- Safety Follow-Up (Day 114 ± 2 or 30 days after Early Termination): a documented phone call to record AEs and concomitant medications (CMs).
- Early termination: In cases of early termination, if a subject has received at least 1 dose (400 mg) of AKST4290 or placebo, the site should try to perform all assessments scheduled at the Visit 6 - EOT visit as well as the subsequent follow up visits unless the subject has withdrawn consent.

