5.8.8 Elevated Liver Enzyme Investigations

Adverse events of abnormal liver enzyme values meeting the following criteria may require additional investigation:

- 
- 
- Drug-Induced Liver Injury

Elevated liver enzyme investigations may include: imaging, repeat lab testing, and review of symptoms, medical history, and exposure to risk factors (e.g. concomitant drug and alcohol use, etc.). All elevated liver enzyme investigations will be provided in listings. The number and percentage of subjects that met the criteria for the above liver enzyme categories will be summarized from the laboratory data.

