5.8.9 Prior and Concomitant Medications

The number and percentage of subjects taking any prior and concomitant medications will be summarized by anatomical therapeutic chemical (ATC) level 3 terms and preferred medication names.

FM DM015.1
Statistical Analysis Plan
AKST4290-211

Rev B
Page 27 of 30

6 Document Version Control

Revision History:

REVISION	RELEASE DATE	AUTHOR	SUMMARY OF CHANGES
A	23Dec2020	[name]	Original release
B	08Apr2021	[name]/[name]	-Modify specification of MMRM model to ANCOVA model, when only baseline and Week 12 data. -Per Sponsor request add ITT population for efficacy tables; add breakdown of each cognitive domain for MoCA, include mean scores for SE-ADL; add breakdown of each parameter for CISI-PD; include overall summaries for abnormal Chemistry lab summary table. -Other minor edits

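### The laboratory summaries in SAP 5.8.3 do not define a per-subject, baseline-relative incidence over the post-dose period, which is what the secondary endpoint in 3.2 calls for

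*SAP*

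**What the plan says.** SAP 3.2 lists as a secondary endpoint "Incidence of abnormalities or clinically-significant changes from Baseline in laboratory test data, vital sign measurements, and electrocardiograms (ECGs".

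SAP 5.8.3 gives a list of three laboratory summaries:

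- observed values at each scheduled visit, with change from baseline at post-baseline visits;
- a by-week cross-tabulation, worded as "Shift tables by treatment group and by out of range flag at Weeks 2, 4, 8, 12, and 14, compared to baseline";
- a subject-level tally, which the plan words as "Number and percentage of subjects with abnormal laboratory tests at all visits".

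It adds that listings will show all collected results with toxicity grades, and that abnormal tests will have their own listing.

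SAP 4.7 treats the visits as nominal for analysis. After early termination, "the site should try to perform all assessments scheduled at the Visit 6 - EOT visit", and the Visit 7 follow-up then falls 14 days after termination. SAP 5.8.8 foresees retesting for liver enzymes ("Elevated liver enzyme investigations may include: imaging, repeat lab testing") and provides one count that is not tied to a visit: "The number and percentage of subjects that met the criteria for the above liver enzyme categories will be summarized from the laboratory data".

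**The concern.** Incidence after dosing is a per-subject quantity: each subject is counted once if an abnormality appears or worsens at any time after the first dose. Shift tables cut by week spread transient abnormalities over several tables, and a reader cannot add them up without knowing whether the same subjects recur. Repeat and unscheduled samples tend to be drawn because something looked wrong, so a table restricted to scheduled weeks may leave out the most informative values. At stake is whether the trial's tables show a declared secondary safety endpoint by arm, or whether the reader has to reconstruct it from listings.

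**Working it through.** The SAP states no laboratory abnormality rate and no expected count, so there is no planned figure to reproduce. The check is a comparison of sections, followed by an illustration.

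**Step 1. Each summary in 5.8.3 against what the endpoint needs.**

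| Summary in 5.8.3 | Relative to baseline | One count per subject over the post-dose period |
|---|---|---|
| Values and changes by scheduled visit | Yes, as changes in value | No |
| Shift tables at five weeks | Yes | No, split by week |
| Count of subjects with abnormal tests | No | Unclear |

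The third row is unclear for two reasons. Its closing phrase can mean a count at each visit or one count across visits. It is also not limited to post-dose visits: 5.8.3 has samples at Visits 1 to 7, and note 4 to the schedule in 4.8 puts the first dose after all Visit 2 assessments, so two of the seven visits are pre-dose. Read as each visit, the row gives no cumulative incidence. Read as any visit, it includes subjects who were already abnormal before dosing and does not separate them. No row satisfies both columns.

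**Step 2. Results outside the scheduled weeks.** Neither 4.7 nor 5.8.3 has a rule for repeat or unscheduled post-dose results. Read literally, they have no place in the shift tables. Early-termination draws differ. Take a subject who stops on Day 40, between Visit 4 (Day 28) and Visit 5 (Day 56). The draw follows the Visit 6/EOT assessments and could be shown under Week 12. The follow-up at 40 + 14 = Day 54 carries the Visit 7 label and could be shown under Week 14. The SAP does not say whether either happens.

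**Step 3. What by-visit counts can and cannot tell.** Inputs: about 60 subjects per arm (SAP 4.4) and five post-baseline visits (SAP 5.8.3). The per-visit rate p of a new abnormality on one test is an assumption, and all subjects are taken to attend all five visits.

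- Expected count in each visit table: 60 × p.
- Share ever affected, same subjects each time: p.
- Share ever affected, visits independent: 1 − (1 − p)^5.

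| Assumed p | Per visit table | Ever affected, same subjects | Ever affected, independent visits |
|---|---|---|---|
| 1% | 0.6 | 1% (0.6) | 1 − 0.99^5 = 4.9% (2.9) |
| 3% | 1.8 | 3% (1.8) | 1 − 0.97^5 = 14.1% (8.5) |
| 5% | 3.0 | 5% (3.0) | 1 − 0.95^5 = 22.6% (13.6) |

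Independence is not quite the arithmetic ceiling. If no subject were abnormal twice, p = 3% would give 5 × 3% = 15%. In every row the same five visit tables fit a wide range of cumulative incidence.

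**The case against.** The strongest reply is that 5.8.3 does contain a subject-level count, and that 3.2 joins abnormalities and changes from Baseline with the word or, so the count can serve the first limb and the shift tables the second. That stands to this extent: a reader might infer that the incidence is not estimated at all, and the documents do not support that. What remains is that the count's time window is undefined and includes pre-dose results, so neither limb receives a post-dose, per-subject figure.

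A reader might also infer that early-termination results drop out. SAP 4.7 does not say so. Those draws are Visit 6/EOT and Visit 7 assessments, so they are unplaced rather than excluded.

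A third tempting reading is that the safety conclusion is biased towards no effect. The arithmetic models no treatment difference, informative dropout or retesting, so it shows no bias. Other outputs also carry part of the signal: 5.8.2 tabulates adverse events once per subject, by worst severity, and summarises those leading to discontinuation; 5.8.8 counts subjects meeting the liver criteria; and the listings keep every result.

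Finally, the table shells are separate files and not at hand. The revision history has an entry to "include overall summaries for abnormal Chemistry lab summary table", so an overall row may exist for chemistry. That entry is not evidence of an error. It names chemistry only, and the text of 5.8.3 defines no such row for any panel.

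**Conclusion.** The point holds as a gap in specification. No laboratory summary defined in 5.8.3 gives a per-subject, baseline-relative incidence over the post-dose period. Repeat and unscheduled results have no rule that brings them into the shift tables, and early-termination draws have no stated week. Signals may be understated in the tables, but the documents do not show by how much. The range of 3% to 14.1% at an assumed 3% per visit shows only that by-visit counts leave the cumulative figure undetermined. The upper figure rests on independence between visits within a subject, which is an extreme case. The primary analysis is unaffected. Because this is a declared secondary safety endpoint and the data are already collected, the change should be made.

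**What to change.** In SAP 5.8.3:

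1. Add a shift table by arm, in the Safety population, from baseline to the worst post-baseline value. Show lowest and highest separately, and worst toxicity grade where one is assigned. Use all post-dose results: scheduled, repeat, unscheduled and early termination.
2. Report, as the laboratory incidence endpoint, the number and percentage of subjects with any abnormality that is new or worse than baseline, each subject counted once. Use this to replace or define the present count of subjects with abnormal tests.
3. Keep the by-visit tables as support.
4. State the analysis week for early-termination draws.

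A matching worst-versus-baseline row in the ECG interpretation table of 5.8.5 is optional.

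The cost is one paragraph and a few tables from existing data. The method has one small downside: subjects retested more often have more chances of an extreme value. A footnote should say so.

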5.8.4 Vital Signs

[figure not shown]
Vital signs, including blood pressure (mmHg), heart rate (beats/min), respiratory rate (breaths/min), and body temperature (C), will be collected at all in-person visits (i.e. Visits 1-7). Observed values will be tabulated at screening, baseline, and at each scheduled post-baseline time point. Change from baseline at each scheduled post-baseline time point will also be summarized by treatment group.

Vital signs at each scheduled time point will also be provided in subject data listings.

5.8.5 12-lead ECG

A 12-lead ECG will be performed to obtain Heart rate (beats/min), QT interval (msec), and QT interval corrected by the Fridericia formula (QTcF). ECGs will be collected at Screening and at Weeks 4 and 12. Observed values, along with the change from baseline at each scheduled post-baseline visit, will be summarized by treatment group. Additionally, a frequency table detailing the overall interpretation of ECG findings will be provided.

A listing of abnormal 12-lead ECG will also be generated.

5.8.6 Physical Examination

Full or targeted physical examinations will be conducted at every in-person study visit (i.e. Visits 1-7). The number and percentage of subjects with abnormal clinically significant and not clinically significant physical examination results will be summarized by the body systems at each scheduled visit.

5.8.7 Pregnancy tests

Pregnancy test results will be provided for women of childbearing potential in a listing only.

5.8.8 Elevated Liver Enzyme Investigations

Adverse events of abnormal liver enzyme values meeting the following criteria may require additional investigation:

- 
- 
- Drug-Induced Liver Injury

Elevated liver enzyme investigations may include: imaging, repeat lab testing, and review of symptoms, medical history, and exposure to risk factors (e.g. concomitant drug and alcohol use, etc.). All elevated liver enzyme investigations will be provided in listings. The number and percentage of subjects that met the criteria for the above liver enzyme categories will be summarized from the laboratory data.

5.8.9 Prior and Concomitant Medications

The number and percentage of subjects taking any prior and concomitant medications will be summarized by anatomical therapeutic chemical (ATC) level 3 terms and preferred medication names.

FM DM015.1
Statistical Analysis Plan
AKST4290-211

Rev B
Page 27 of 30

6 Document Version Control

Revision History:

REVISION	RELEASE DATE	AUTHOR	SUMMARY OF CHANGES
A	23Dec2020	[name]	Original release
B	08Apr2021	[name]/[name]	-Modify specification of MMRM model to ANCOVA model, when only baseline and Week 12 data. -Per Sponsor request add ITT population for efficacy tables; add breakdown of each cognitive domain for MoCA, include mean scores for SE-ADL; add breakdown of each parameter for CISI-PD; include overall summaries for abnormal Chemistry lab summary table. -Other minor edits

Appendix A - Programming Specifications for Tables and Listings

The following specifications will be used in the production of tables and listings.

1. Page Setup

Unless otherwise noted, tables and listings will use landscape orientation. Margins will be at least 3/4 of an inch on the left side of page, at least 3/4 of an inch at the top, and 3/8 of an inch on the other sides.

Upper left: Sponsor name and protocol number

- Center: CONFIDENTIAL; Database Download Date: ddmmmyy
- Upper right: Page number shown as Page n of N. Page numbers should be sequential within a table or listing.

The footer should include:

- Left: the name of the SAS program used to generate the output
- Center: run date/time and the words “by CTDS”.
- Right: output file name.

2. Footnotes

Unless otherwise specified, footnotes should appear on all pages within the table.

3. Font

Font will be 9-point Arial, or smaller if needed for space constraints. If possible, small tables should appear on one page. If tables continue on to multiple pages, there should be a page break after an assessment so that all the statistics for an assessment appear on the same page.

4. Tables

Table titles should reflect the content of the table. Under the main title, in parentheses, the name of the analysis population being summarized should appear.

Summary Statistics - Continuous Data

Unless otherwise noted, the mean and median and confidence interval (CI) of a set of values should be printed out to one decimal place more than the original value. The standard deviation and standard error should be printed out to 2 decimal places more than the original value. The number of subjects on whom the parameter is assessed should appear. Minimum and maximum should be consistent with the original value.

Summary Statistics - Categorical Data

Numbers of subjects are reported as whole numbers. Null counts are represented as 0. Table percentages should be reported to one decimal unless otherwise noted. Null percentages should be reported as 0.0. For all categories, the total number of subjects with data will be presented as N.

FM DM015.1
Statistical Analysis Plan
AKST4290-211

Rev B
Page 29 of 30

5. Subjects Included in Listings

